| | 
from the date of signed informed consent (enrollment) until end of study, which includes withdrawal of consent, loss to follow-up, death, or study completion. Continuation in the study is not contingent on continuation of Valchlor.
 
Patients currently enrolled and ongoing or newly enrolled will be offered to participate in the 24-month study of this protocol Amendment 1. Patients who enrolled under the original protocol (prior to Amendment 1) and are still ongoing in the study will be re-consented and to follow data collection specified in Table 1 of this protocol for a total of 24 months from original consent date. Patients who enrolled and have completed 1 year of the study under the original protocol will not be re-consented under Amendment 1.
 |
| 
POPULATION (SETTING AND STUDY POPULATION)
 | 
This study will enroll approximately 300 consecutive patients diagnosed with MF-CTCL and being treated with Valchlor, regardless of other MF-CTCL therapies received before or at enrollment. Patients will be enrolled from up to 50 participating centers/clinics in university-affiliated or community hospitals in the US. The participation of physicians and patients in the study is on a voluntary basis.
 
Inclusion criteria:
 
 • All adult patients (≥ 18 years of age) diagnosed with MF-CTCL and being treated with Valchlor. This includes patients newly initiating Valchlor OR patients continuing treatment with Valchlor: 
 ○ Patients newly initiating Valchlor are patients who have their first office visit after having initiated Valchlor. ○ Patients continuing treatment with Valchlor includes patients who are actively taking Valchlor on the day of enrollment. ○ Signed patient informed consent. 
Exclusion criteria:
 
 • None |
| 
VARIABLES
 | 
The variables of interest for this study includes clinical characteristics, treatment patterns, clinical status, as assessed by the physician (including the methods used in practice to assess clinical status), MF-CTCL-related healthcare utilization, as assessed by the physician (hospitalizations and emergency room visits), AEs and
 |

| | |
|--|---|

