5.5 Study size

This study will have an approximate enrollment of 300 patients diagnosed with MF-CTCL who are being treated with Valchlor (newly initiated or continuing treatment).

A sample size of 270 evaluable patients is needed to estimate the percentage of patients with clinical status and the percentage of patients with hospitalizations, both with a margin of error of 6 percentage points. Assuming that up to 10% of patients may be non-evaluable due to incomplete follow-up, the sample size target for enrollment should be 300.

It is projected that approximately 200 evaluable patients will be re-consented under Amendment 1. The margin of error for 200 evaluable patients will be 7%.

Additionally, it is important to be able to estimate these same percentages with a margin of error of 10 percentage points or less for key subgroups representing a third or more of the patient population (e.g., patients newly initiating Valchlor). A total of 100 patients are required to achieve a margin of error of 10 percentage points per subgroup, so that a total enrollment of 300 patients is needed.

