5.6 Data management

5.6.1 Data collection

Informed consent must be obtained prior to enrollment and data collection.

Re-consent must be obtained for patients that were enrolled in the study prior to Amendment 1 and still ongoing to complete 24 months of data collection from the enrollment date. Instead of the 12 months initially planned.

This study will collect data on MF-CTCL patients being treated with Valchlor [see Section 5.2.1 for inclusion criteria] under routine clinical care. This will include both data collected from assessments that are routinely performed for MF-CTCL patients being treated with Valchlor in clinical practice, and additional data from further assessments that may be performed.

No specific clinically mandated assessments are to be performed as part of study participation. Patient-completed questionnaires, however, are a study requirement and will be collected at all clinic visits during the study observation period. These questionnaires will be administered on paper by study coordinators. Patient clinical data (non-patient-completed) will be collected from the patient's medical records at enrollment and throughout the study period. All data will be entered into an eCRF at the time of collection or on a quarterly basis by study coordinators. AEs, reports of secondary exposure, and SAEs whether or not related to Valchlor will be entered into the eCRF at every visit and upon notification by the patient (e.g., reported via phone call).

A secure, Internet-based electronic data collection (EDC) system will be used for data entry and hosting. An audit trail will be maintained by the EDC system for all data entries and changes, indicating what entries/changes have been made, who made them, and when. Data will be encrypted when transferred over the Internet and will be stored in a secure database protected from unauthorized access.

All data collected will be de-identified before transmission to the central study coordinating center. Patient names will not be collected. Other patient identifiers will be collected in order to allow identification of study patients when SAEs are received by US Drug Safety outside of the study [see Section 7.4].

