5.9 Discussion of the study methods (including limitations)

This study is an observational, prospective study examining MF-CTCL patients being treated with Valchlor in a real-world clinical setting. Valchlor treatment will be based on prescriber decision and will not be influenced by participation in this study. The patients will be followed by their physician according to routine clinical practice. The study protocol does not mandate any treatment, procedures or visits. Patient-completed questionnaires, however, are a study requirement and will be administered at all study visits for patients who can read and understand English, and are physically and mentally able to complete the questionnaires based on the investigator's assessment.

Any interpretation of observational study results should consider limitations to observational real-world study designs, including potential sources of selection or information biases, and confounding factors.

To minimize selection bias, participating centers will offer enrollment in the study to all consecutive MF-CTCL patients currently treated with Valchlor [see Section 5.2.1 for inclusion criteria], regardless of other MF-CTCL specific therapy received before or at

the time of enrollment, or during the study. This study collects data on all users of Valchlor. At enrollment, a review of existing medical records will be performed to collect information as described per [Table 1](#) (enrollment visit). Thereafter, all data will be collected during the observation period.

Patients who are enrolled under the original protocol prior to protocol Amendment 1 and are still ongoing in the study will be re-consented under Amendment 1 and will continue to follow the schedule of Table 1 eCRF Data Collection specified in this protocol up to end of study (Month 24). Patients who enrolled and have completed 1 year of the study under the original protocol will not be offered to continue in the study and thus not re-consented under Amendment 1.

To minimize the number of patients lost to follow-up, there will be regular contact with patients by the site, including 3 attempts to contact a patient before she/he is considered lost to follow-up.

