The by-time analyses for each visit will provide supportive clinical and statistical mechlorethamine response data over the whole treatment period, before and after the 12 month results. Patient visits were variable throughout the study and no defined patient visits were required in PROVe. Given this construct, the By-Visit analyses of % BSA data, Pruritis VAS, Skin-Dex 29, and the MF/SS CTCL QOL instrument will be constructed from the respective change from baseline that occurred closest to each of the following timepoints 1, 3, 6, 9, 12, 15, 18, 21 and 24 months, and will include data that falls within  $\pm 45$  days of each designated timepoint.

Other secondary endpoints include:

- Overall Response Rate 2 (ORR2) Percent of patients with  $\geq 50\%$  reduction from baseline in % Body Surface Area of disease for at least two consecutive visits.
- Overall Response Rate 4 (ORR4) Percent of patients with  $\geq 50\%$  reduction from baseline in % Body Surface Area of disease for at least four consecutive visits.
- Time to Next Treatment (TTNT). TTNT is defined as the median number of days an individual patient stayed on a treatment before starting a new treatment or adding on an additional treatment.
- Rates of on Study Hospitalization
- Pruritis VAS
- SkinDex-29

- MF/SS CTCL – QOL Instrument

For each endpoint, separate analyses will be done for patients contributing data with IA and IB staging, all staged patients, and all patients regardless of staging. As PROVe is an observational study, an Intent-to-Treat (ITT) population analysis is not applicable. There are no cases where an intention to treat was prevented and therefore no potential for a selection bias in the analyses prespecified in this SAP. This results in a total of 51 analysis types as shown in the Figure 1 below.

Figure 1: Analysis Populations for the PROVe Study

	Patients Contributing Data			Totals:
	IA and IB Staging	All Staged	All Patients with and without Staging	
Primary Endpoint	1	1	1	3
9 By-Time Analyses	9	9	9	27
7 Other Secondary Endpoints	7	7	7	21
			Overall Total:	51

These analyses will be applied to following four (4) analysis populations:

1. Valchlor + corticosteroids + possibly another treatment (primary) (V+C+other)
2. Valchlor + phototherapy + possibly another treatment (V+P+other)
3. Valchlor + oral bexarotene + possibly another treatment (V+B+other)
4. Valchlor + any other treatment (V+other)

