Completing 12 months	N (%)
Completing 15 months	N (%)
Completing 18 months	N (%)
Completing 21 months	N (%)
Completing 24 months	N (%)

Run Date: ddMMMyyyy

Date of Data Extraction: ddMMMyyyy

Helsinn Therapeutics (US), Inc.,  
 Protocol AC-079A501 (PROVe)  
 Table 1B. Completed Visits

Patient Count (n=x)	Enrollment	Ongoing	Early Termination
	x	Visit 1 = x (%)	x
		Visit 2 = x (%)	Patient Withdrew Consent = x (%)
		Visit 3 = x (%)	Patient Lost to Follow-Up = x (%)
		Visit 4 = x (%)	Adverse Event = x (%)
		Visit 5 = x (%)	Physician's Decision to Withdraw = x (%)
		Visit 6 = x (%)	Missing data = x (%)
		Visit 7 = x (%)	
		Visit 8 = x (%)	
		Visit 9 = x (%)	
		Visit 10 = x (%)	
		Visit 11 = x (%)	
		Visit 12 = x (%)	
		Visit > 12 = x (%)	

Run Date:  
 ddMMMyyyy  
 Date of Data Extraction: ddMMMyyyy

Table 1C. Exposure Duration to Valchlor and Other MF-CTCL Therapies

Patient Count = N Number of Patients x (%)	Number of Patients Received 3 months Treatment	Number of Patients Received 6 months Treatment	Number of Patients Received 9 months Treatment	Number of Patients Received 12 months Treatment	Number of Patients Received 15 months Treatment	Number of Patients Received 18 months Treatment	Number of Patients Received months Treatment
Valchlor							
SKIN DIRECTED THERAPIES:							
Phototherapy UVB							
Phototherapy nbUVB							
Phototherapy PUVA							
Radiation Therapy, local, localized electron beam radiation							
Radiation therapy, local TSEBT							
Chemotherapy, topical, Carmustine, topical (BICNU)							
Chemotherapy, topical Other							
Corticosteroids, topical							
Retinoids, Topical Bexarotene (Targretin)							
Retinoids, Topical, Tazarotene (Tazorac, others)							

Retinoids, Topical, Other							
Topical imiquimod (Aldara, others)							
Other topical: specified							
SYSTEMIC THERAPIES:							
Chemotherap y, systemic, Bortezomib (Velcade)							
Chemotherap y, systemic, Chlorambucil (Leukeran)							
Patient Count = N Number of Patients x (%)	Number of Patients Received 3 months Treatment	Number of Patients Received 6 months Treatment	Number of Patients Received 9 months Treatment	Number of Patients Received 12 months Treatment	Number of Patients Received 15 months Treatment	Number of Patients Received 18 months Treatment	Number of Patients Received months Treatment
Chemotherap y, systemic, Cyclophospha mide (Cytoxan, others)							
Chemotherap y, systemic, Doxorubicin, liposomal (Doxil)							

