	IA and IB Staging	All Staged	All patients with and without Staging
	N=	N=	N=
V+C+Other			
V+P+Other			
V+OB+Other			
V+C+P+Other			
V+C+P			
V+Other			

Table 21a. Percent of patients with  $\geq 50\%$  reduction from baseline in % Body Surface Area of disease in 12 months – All Patients

Helsinn Therapeutics (US), Inc.,  
 Protocol AC-079A501 (PROVe)

Table 22. Percent of patients with  $\geq 50\%$  reduction from baseline in % Body Surface Area of disease at each visit preceding and following the 12 month visit, including months 1, 3, 6, 9, 12, 15, 18, 21 and 24  $\pm$  45 days.

	IA and IB Staging	All Staged	All patients with and without Staging
Month 1	N=	N=	N=
V+C+Other			
V+P+Other			
V+OB+Other			
V+C+P+Other			
V+C+P			
V+Other			
Month 3	N=	N=	N=
V+C+Other			
V+P+Other			
V+OB+Other			
V+C+P+Other			
V+C+P			
V+Other			
Month 6	N=	N=	N=
V+C+Other			
V+P+Other			
V+OB+Other			
V+C+P+Other			
V+C+P			
V+Other			
Month 9	N=	N=	N=
V+C+Other			
V+P+Other			
V+OB+Other			
V+C+P+Other			
V+C+P			
V+Other			
Month 12	N=	N=	N=
V+C+Other			
V+P+Other			
V+OB+Other			
V+C+P+Other			

V+C+P			
V+Other			
Month 15	N=	N=	N=
V+C+Other			
V+P+Other			
V+OB+Other			
V+C+P+Other			
V+C+P			
V+Other			
Month 18	N=	N=	N=
V+C+Other			
V+P+Other			
V+OB+Other			
V+C+P+Other			
V+C+P			
V+Other			
Month 21	N=	N=	N=
V+C+Other			
V+P+Other			
V+OB+Other			
V+C+P+Other			
V+C+P			
V+Other			
Month 24	N=	N=	N=
V+C+Other			
V+P+Other			
V+OB+Other			
V+C+P+Other			
V+C+P			
V+Other			

Helsinn Therapeutics (US), Inc.,  
 Protocol AC-079A501 (PROVe)

Table 23. Overall Response Rate 2 (ORR2) Percent of patients with  $\geq 50\%$  reduction from baseline in % Body Surface Area of disease for at least two consecutive visits

	Patients Contributing Data		
	IA and IB Staging	All Staged	All patients with and without Staging
	N=	N=	N=
V+C+Other			
V+P+Other			
V+OB+Other			
V+C+P+Other			
V+C+P			
V+Other			

Helsinn Therapeutics (US), Inc.,  
 Protocol AC-079A501 (PROVe)

Table 24. Overall Response Rate 4 (ORR4) Percent of patients with  $\geq 50\%$  reduction from baseline in % Body Surface Area of disease for at least four consecutive visits

	Patients Contributing Data		
	IA and IB Staging	All Staged	All patients with and without Staging
	N=	N=	N=
V+C+Other			
V+P+Other			
V+OB+Other			
V+C+P+Other			
V+C+P			
V+Other			

Helsinn Therapeutics (US), Inc.,  
 Protocol AC-079A501 (PROVe)

Table 25. Time to Next Treatment (TTNT)

	Patients Contributing Data		

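### The SAP presents months 1 to 24 as one series although only patients consented under Amendment 1 can be observed after month 12, so part of any change across month 12 may reflect a change of cohort

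*SAP*

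**What the plan says.** The original protocol planned one year of follow-up. Amendment 1 extends this to 24 months from consent for new enrollees and for ongoing patients who re-consent (protocol section 5.6.1: "Instead of the 12 months initially planned"). Section 5.9 closes the extension to those who had already finished: "Patients who enrolled and have completed 1 year of the study under the original protocol will not be offered to continue in the study". The synopsis gives the same rule.

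The protocol treats the two-year patients as a set of their own. Section 5.5 says: "It is projected that approximately 200 evaluable patients will be re-consented under Amendment 1". It gives that set a margin of error of 7 points, against 6 points for the 270 evaluable patients overall. The synopsis words the 200 differently and counts new enrollees together with re-consented patients.

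The SAP does not carry this split forward. Under Analysis Populations it sets nine timepoints from month 1 to month 24, each with a window of ±45 days, and describes the result as "supportive clinical and statistical mechlorethamine response data over the whole treatment period, before and after the 12 month results". Table 22 reports BSA response "at each visit preceding and following the 12 month visit, including months 1, 3, 6, 9, 12, 15, 18, 21 and 24", and Tables 27a to 27c apply the same timepoints to the patient-reported outcomes. Table 1A has N (%) rows from 3 months up to "Completing 24 months", under one N and with no denominator stated. No table is split by consent version, and the Analysis Populations section denies that selection bias can arise in the prespecified analyses.

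**The concern.** Around month 12 the set of patients who can be observed changes by rule. Patients who finished under the original protocol drop out of view, and ongoing patients stay in view only if they re-consent. Re-consenters also had to be still in the study when the amendment came into force, so the later set is partly selected on staying in the study.

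A reader of Table 22 or Table 27 will naturally follow the values from month 12 to month 15 and beyond. If the two cohorts differ in response or symptom scores, the series can move with no patient changing. In Table 1A, patients who completed the follow-up they agreed to may count as not completing months 15 to 24. The statement on selection bias gives no warning of either.

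**Working it through.** **1. The plan's own precision figures.** Margin of error = 1.96 × √(0.25/n). This assumes a 95% two-sided interval and a proportion of 0.5, neither of which is stated.
- n = 270: 5.96 points (stated 6)
- n = 200: 6.93 points (stated 7)
- n = 100: 9.80 points (stated 10)
- Enrollment: 270/0.90 = 300 (stated 300)

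All four reproduce, so the 200 and the 270 are taken as the plan's working figures.

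**2. Where the cut falls.** With months of 365.25/12 days and ±45 days, month 12 covers days 320 to 410 and month 15 covers days 412 to 502. Counted from enrollment, a patient whose follow-up ends at 12 months can contribute to month 12 but not to months 15 to 24. The SAP does not say whether months run from enrollment or from a pre-Valchlor baseline. If from baseline, the cut is blurred for continuing patients, whom the SAP puts on average 3 months apart from new users. It is not removed.

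**3. Share in the two-year set.** Evaluable patients: 200/270 = 74.1% in the set and 70/270 = 25.9% outside it. On enrolled patients, with the same 10% allowance: 200/0.90 = 222, and 222/300 = 74.1%. The two bases agree when numerator and denominator are of the same kind.

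**4. Effect on the by-time series.** Suppose no patient's response changes and the 25.9% share also holds among the month 12 contributors. The series then moves by 0.259 × (response in the followed cohort − response in the cohort not followed). The documents give no cohort difference, so these values are assumptions:

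| Assumed difference | Shift after month 12 |
|---|---|
| 5 points | 1.3 points |
| 10 points | 2.6 points |
| 20 points | 5.2 points |
| 30 points | 7.8 points |

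The sign depends on which cohort responds better.

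**5. Effect on Table 1A, if all patients are the denominator.** Shown completion = true completion among those consented to 24 months × 0.741.

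| True | Shown |
|---|---|
| 100% | 74.1% |
| 90% | 66.7% |
| 80% | 59.3% |
| 70% | 51.9% |

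If the share outside the two-year set were 10%, 33% or 50%, a true 90% would show as 81%, 60% or 45%.

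**The case against.** The case on the other side has real force, and several stronger readings should be set aside.

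- *Retention is understated.* A reader might infer this from Table 1A, but the table states no denominator and is titled as person-months on study. Understatement follows only if all patients are used.
- *Finishers will pass for drop-outs.* The SAP also plans a table of discontinuation reasons and a disposition listing that includes completed patients. Table 1B counts early terminations by reason, and planned completion is not among the named reasons. Those outputs limit the misreading but leave the percentages in Table 1A as they are.
- *Months 1 to 12 describe all enrollees.* They do not. Each point covers patients in a given concomitant-therapy population with a verified baseline and a value in the window. Visits are unscheduled, so contributors vary at every timepoint. Month 12 differs because a known group leaves there by rule.
- *The trend is biased.* No contrast between months 12 and 15, slope or longitudinal model is planned. The p-values are descriptive, and the Table 22 and Table 27a shells print N for each month. The documents support a possible contribution from the change of cohort, not a demonstrated bias.
- *Completion cannot exceed 67% (200/300).* This sets evaluable patients over enrolled patients. Like for like, the cap is 74%.
- *All 70 are lost by design.* Some may be active patients who decline to re-consent.

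For results considered for external dissemination, the SAP requires a comparison of patients who did and did not contribute data. That helps, but it is not made by consent version. A monthly N shows that numbers fall, not why.

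Table 27c is probably the least affected. Protocol section 1 says the amendment added a quality-of-life assessment. If that is the MF/SS-CTCL questionnaire, original-protocol completers have no data on it at any month.

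**Conclusion.** The point holds as a limit on interpretation and a gap in presentation. The change in who can be observed after month 12 is certain from the protocol, and the SAP neither shows nor acknowledges it. Each monthly value remains valid for its contributors. What cannot be read directly is a change across month 12, because part of it may come from the change of cohort. The direction and size of that part cannot be determined from the documents, and the 1.3 to 7.8 points above rest wholly on assumed cohort differences.

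For Table 1A the conclusion is conditional. With all patients as denominator, apparent 24-month completion is capped at about 74%, and true retention of 80% would show as about 59%. This rests on a projected 200, not an actual count. On the wording of section 5.5, which mentions re-consented patients only, new enrollees would come on top and the cap would be higher. The point does not bear on the definition of the primary 12-month endpoint.

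**What to change.** 1. In Tables 22 and 27a to 27c, add a set of values at all nine timepoints limited to patients consented to 24-month follow-up, at least for the primary population (Valchlor plus corticosteroids plus possibly another treatment) and subject to the SAP's sample-size thresholds. Interpret trends across month 12 only within that set. In Table 27c it may largely repeat the existing values.
2. In Table 1A, state the denominator. For months 15 to 24, use the patients consented to 24-month follow-up, and show original-protocol 12-month completers on their own line as *completed as planned*.
3. Under Analysis Populations, replace the denial of selection bias with a sentence acknowledging that the observable cohort changes after month 12.

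No new data are needed, because the consent and re-consent dates define the set. The cost is SAP wording, extra columns and smaller cells. Table 28 shows 88 patients on topical corticosteroids, 33 on phototherapy and 36 on systemic retinoids during treatment. At 74.1% these become about 65, 24 and 27, before stage, baseline and window requirements. Some cells will fall below the 20 needed for a statistical analysis, which is why the primary population comes first.

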## ANALYSIS POPULATIONS

This study will enroll approximately 300 MF-CTCL patients who are being treated (newly initiated or continuing treatment) with Valchlor from up to 50 participating university-affiliated hospitals, community hospitals, or community clinics in the United States.

Patients considered 'being treated with Valchlor' are composed of two distinct groups:

- 1) Patients who are newly initiating Valchlor treatment (i.e. patients who have initiated Valchlor within 30 days or fewer prior to enrollment) and,
- 2) Patients who are continuing treatment with Valchlor (i.e. patients who have been on Valchlor for more than 30 days prior to enrollment).

Patients in either group must be treated with Valchlor at enrollment to be eligible for the study.

All consecutive MF-CTCL patients who are receiving Valchlor at participating US centers are eligible for enrollment in the study, regardless of other MF-CTCL therapies received before or at the time of enrollment.

The primary efficacy endpoint will be the proportion of subjects who are responders to treatment at the 12-month timepoint using a  $\geq 50\%$  reduction from baseline in BSA as the definition of a responder in the group of patients who used mechlorethamine plus corticosteroids and possibly another treatment. Since PROVe did not require a specific visit schedule, the primary 12-month analysis will include patients with a post-baseline % BSA score that falls within a window of  $365 \pm 90$  days. Please note that in this observational trial, patients continued on study even if they permanently discontinued mechlorethamine gel for any reason and switched to new therapy. Given this, such patients (15-20%) will be excluded from the analysis at 12 months. A sensitivity analysis will be conducted for the primary analysis using the full dataset. We will compare this to the subset of patients who discontinued mechlorethamine gel (Table 21a).

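### The SAP plans two unreconciled 12-month BSA response rates: the primary has no rule for choosing among several scores, and the switch exclusion is stated for the 12-month analysis only

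*SAP*

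**What the plan says.** All of this is in the SAP, mostly under Analysis Populations.

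- **Primary (Table 21).** Because PROVe set no visit schedule, "the primary 12-month analysis will include patients with a post-baseline % BSA score that falls within a window of" 365 ± 90 days. Patients who permanently stopped the gel and moved to a new therapy stayed on study, and "such patients (15-20%) will be excluded from the analysis at 12 months".
- **Sensitivity (Table 21a).** "A sensitivity analysis will be conducted for the primary analysis using the full dataset". The result is then compared with the subset who discontinued the gel.
- **By-time (Table 22).** The planned "timepoints 1, 3, 6, 9, 12, 15, 18, 21 and 24 months" include Month 12. The results "will be constructed from the respective change from baseline that occurred closest to each of the following timepoints", and the analysis "will include data that falls within $\pm 45$ days of each designated timepoint". The text offers these results as supportive mechlorethamine response data across the whole treatment period.
- **ORR2 and ORR4 (Tables 23 and 24).** These require a reduction of at least 50% at two or four consecutive visits. No rule is given for visits after a switch.
- **Default.** The Statistical Methods section uses all patients in the analysis population unless something else is specified.

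**The concern.** A reader will set the Month 12 row of Table 22 beside Table 21 and expect the two to agree. They may not, for reasons the SAP does not mention: the windows differ, only one has a rule for picking a score, and possibly only one leaves out switchers. A BSA on day 300 counts as 12 months in Table 21 but can only count as Month 9 in Table 22.

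Two things are at stake. First, with several scores in a 181-day window and no selection rule, the primary percentage is not fixed by the plan and could be settled after the data have been seen. Second, tables presented as support for a mechlorethamine response would include skin scores taken on a different therapy.

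**Working it through.** **1. Are two 12-month analyses really planned?** SAP Figure 1 gives a total of 51. Three staging sets × (1 primary + 9 by-time + 7 other secondary) = 3 × 17 = 51, which reproduces it. If Month 12 were not a separate by-time analysis, the total would be 3 × (1 + 8 + 7) = 48. So both are planned, although Table 22's title speaks of visits before and after the 12-month visit.

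**2. The outputs side by side**

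| | Table 21 | Table 21a | Table 22, Month 12 |
|---|---|---|---|
| Window | 365 ± 90 days | none in title; the text makes it the primary analysis | ± 45 days |
| Several scores | no rule | no rule | closest |
| Stop-and-switch patients | excluded | included | not stated |

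The rule under Clinical Status Assessments / Response, that one positive measure makes a responder, covers several measures at one visit. It does not cover several visits.

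**3. How the windows overlap.** The primary window runs from 365 − 90 = 275 to 365 + 90 = 455, which is 455 − 275 + 1 = 181 days. The SAP does not define a month in days, so I tried more than one convention.

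| Convention | Month 9 | Month 12 | Month 15 | No window |
|---|---|---|---|---|
| 365/12-day months, nearest timepoint | 45 | 91 | 45 | 0 |
| 365/12-day months, strict ± 45 | 44 | 91 | 44 | 2 |
| 30-day months, nearest timepoint | 41 | 90 | 50 | 0 |

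In the strict row, Month 9 is 273.75 ± 45 and ends at 318.75. Month 15 is 456.25 ± 45 and starts at 411.25. Days 319 and 411 therefore belong to no by-time window. Days labelled Month 9 or Month 15:

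- strict: 88/181 = 48.6%
- nearest timepoint: 90/181 = 49.7%
- 30-day months: 91/181 = 50.3%

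**4. From days to patients (assumption).** The SAP gives no visit spacing. I simulated evenly spaced visits (SD 0 or 20 days) with a BSA at each, and took the score closest to day 365.

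| Assumed spacing (days) | Closest score outside ± 45 | More than one score in ± 90 |
|---|---|---|
| 60 | 0-1% | about 100% |
| 90 | 0-9% | 87-100% |
| 120 | 25-26% | 50% |
| 150 | 40% | 20-21% |
| 180 | 48-51% | 0-5% |

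With frequent visits the missing selection rule matters most. With sparse visits the window width matters most.

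**5. What the missing rule can do (assumption).** Take patients with two scores in the window, each with a 50% chance of response, and let a be the proportion of patients whose two scores agree. Counting any response gives 1 − a/2, requiring both gives a/2, and taking the closest gives 50%.

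- a = 0.9: 55% (any) and 45% (both)
- a = 0.8: 60% and 40%
- a = 0.7: 65% and 35%

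**6. Who is counted outside the primary.** The exclusion is written for the 12-month analysis. If that means Table 21 only, the Month 12 row of Table 22 keeps switchers. If it also covers that row, they leave at Month 12 and return at Month 15. On either reading nothing is specified for Months 15 to 24, ORR2 or ORR4, so the all-patients default applies.

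For scale only, including a fraction f of switchers lowers the rate by f × (difference in response). With f = 0.15 to 0.20 and assumed differences of 0, 20, 40 and 60 points, that is 0, 3-4, 6-8 and 9-12 points. If switchers respond better, the sign reverses.

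**The case against.** Much can be said for the plan. The wide primary window has a stated reason, the lack of a visit schedule. With timepoints mostly three months apart, ± 45 days is about the width that keeps neighbouring windows from overlapping, and a single primary timepoint has no such limit. The tables are labelled primary, sensitivity and supportive and share one responder definition. Table 21 against Table 21a will already show the effect of including switchers at 12 months. The SAP calls its p-values descriptive, and protocol section 5.7.4 says the response summary does not estimate efficacy. Describing the by-time results as mechlorethamine response might also signal that on-treatment data were intended.

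These points stand as far as they go: different widths are not in themselves an error. They do not supply a selection rule for the primary or a switcher rule for Tables 22-24. The SAP also names a primary efficacy endpoint, so that number should be fixed in advance.

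Three stronger readings are tempting but not supported:

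- **Table 21a uses another endpoint.** Its title says "Body Surface Area of disease in 12 months", which could suggest any response up to that point. But the SAP's list of tables words Table 21 the same way while its shell says 'at', and the text defines 21a as the primary analysis on the full dataset. This is a title slip.
- **Half the patients carry the wrong month.** The half is calendar days. In the simulation the patient share runs from about 0% to about half.
- **The two rates conflict.** The documents hold no results. The rates are different and unreconciled, and the size and direction of any gap are unknown.

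**Conclusion.** The point holds as a should-fix. The SAP defines two 12-month BSA response rates with different windows and selection rules and does not say how they relate. The primary leaves open which score counts. As written, Table 22 for at least Months 15 to 24, and ORR2 and ORR4, include BSA measured after Valchlor was stopped and replaced. For the Month 12 row the handling of switchers is simply unstated.

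The firm size is 88 to 91 of 181 primary-window days outside Month 12, nearly all of them labelled Month 9 or Month 15. It rests only on the stated windows and the month-length convention. The patient shares and percentage-point effects rest on assumed visit spacing, agreement and response rates, and show scale only.

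**What to change.** - In Tables 21 and 21a, use the BSA closest to day 365 within ± 90 days, the same closest-value rule as Table 22, with a tie-break.
- State the switcher rule for Tables 22-24, including the date as of which a patient counts as switched. Show an on-Valchlor version, with the primary's exclusion, beside an all-follow-up version.
- Add a ± 45-day sensitivity analysis of the primary in the same population with the same exclusion. Report how many patients drop out for lack of a score in the narrower window.
- Report the median actual day of assessment in each table.
- Title Tables 21 and 21a 'at 12 months' throughout (clerical only).

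The cost is SAP wording, some programming, a few extra table rows, and smaller N in the on-Valchlor versions. Those versions are also a more selected group, which is why the all-follow-up version belongs beside them. No new data are needed.
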